testing will be performed on that day. Further testing may be required to investigate a finding or guide subject management based on the investigators clinical judgment. Subjects' parent(s)/LAR(s) will be instructed to contact the investigator/study staff if their child presents symptoms of spontaneous bleeding or easy bruising or if their child develops a rash in the month following vaccination, in order to detect any thrombocytopenic petechiae or purpura. The investigator will, based on his/her medical judgement, appropriately investigate infants with clinical suspicion of low platelets.

- Refer to Section 6.6.11.2 and Figure 2 for information about the re-testing of samples in case of any Grade 1 abnormality with potential clinical relevance or any \geq Grade 2 abnormality.
- Blood sample for **RSV serostatus** will be taken from all infants at Screening.
- Blood samples for **CMI** are limited to those in investigational sites with a laboratory in proximity capable to perform WBS necessary for the CMI assay. In those sites, samples will be taken from all subjects at Screening and on Day 30, Day 60, and Day 365.

Note: Blood samples for CMI taken on Day 7 and Day 37 for subjects enrolled under protocol amendment 1 will still be assessed for CMI.

- Blood samples for **humoral immunogenicity** will be taken from all subjects at Screening and on Day 30, Day 60, and Day 365.
 - Blood sample for **assessment of mechanism of illness (potential ERD)** will be taken from subjects hospitalized for LRTI (only for RSV-positive subjects using a locally available RSV test).
 - Nasal swab: there will be monthly nasal swab to detect asymptomatic RSV infections during the RSV season and if following active or a passive surveillance contacts, a subject presents symptoms of RTI, a nasal swab will be collected.

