^e At Screening, for infants with hematological/biochemical values out of normal range which are expected to be temporary, a re-screening visit may be scheduled during which blood sample collection for hematology/biochemistry will be repeated (maximum one re-screening visit per infant is allowed; blood for CMI response and humoral response will not be re-sampled at the re-screening visit, if already done before).

^f If any Grade 1 abnormality with potential clinical relevance (according to investigators judgment) or any ≥ Grade 2 abnormality is detected, or for further evaluation of clinical suspicion of low platelet count, refer to Section 6.6.11.2 and Figure 2 for re-test.

^g Blood samples to be taken before vaccination.

^h If during passive or active surveillance contact, the investigator/study staff assesses that an infant presents a potential RSV-RTI (refer to Table 4 for definition), the potential RSV infection will be assessed by quantitative RT-PCR.

ⁱ Only when the unscheduled visit occurs within the AE reporting time frame, i.e. from Day 0 to Day 6 for solicited AEs and from Day 0 to Day 29 for unsolicited AEs.

^j Signs and symptoms to be recorded in the eCRF are listed in the SPM.

^k Subject's parent(s)/LAR(s) will be instructed to record on the RTI episode card the start date and the end date of the following symptoms (cough, runny nose, blocked nose, difficulty in breathing, or wheezing) and to return it to the investigator at the next visit or by mail (e-mail or postal mail).

^l Blood sample collected for subjects hospitalized for LRTI (only for RSV-positive subjects using a locally available RSV test); Refer to Section 6.7.3.

^m Nasal swab collected at the monthly surveillance for asymptomatic RSV-RTI will be tested by quantitative RT-PCR.

ⁿ For RSV testing and respiratory viral panel (RVP) at a local routine laboratory, where available.

^o In investigational sites with a laboratory in proximity capable to perform WBS necessary for the CMI assay.

^p Day 7 hematology testing will be performed if any ≥ Grade 1 for platelet decrease is detected on Day 1 after vaccination. Similarly, hematology testing on Day 37 will be performed if any ≥ Grade 1 for platelet decrease is detected on Day 31.

CONFIDENTIAL

204838 (RSV PED-002)

Protocol Amendment 4 Final

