Additional viral diagnosis testing on the nasal swabs, such as (but not limited to) multiplex PCR and/or high-throughput sequencing, may be done, if deemed necessary, provided specific assays become available at GSK Biologicals' laboratory or a laboratory designated by GSK Biologicals.

Additional testing may include, but is not limited to, the following:

- Anti-vector immunity: neutralization.

For subjects hospitalized for LRTI and RSV-positive using a locally available RSV test (refer to Section 9.2.5), an additional blood sample will be collected. The corresponding serum sample will be stored at GSK Biologicals laboratory to further characterize the mechanisms of illness (potential ERD), if deemed necessary. In this event, the serum samples could be tested by RSV neutralization assay and also by ELISA (or alternative method) for measurement of protein F antibodies and cytokines.

Hematology and biochemistry assessments will be performed in the investigator’s laboratory as per local practice using standardized and validated procedures (Table 11).

Table 11 Hematology and biochemistry tests (Amended 10 December 2017)

System	Discipline	Component	Timepoint	Method	Scale	Laboratory
Whole blood	Hematology	Hemoglobin	Screening, Day 1, Day 7*, Day 30, Day 31, Day 37*, Day 60	As per local practice	Quantitative	Local laboratory
		Leukocytes (White Blood Cells)**				
		Platelets				
Serum	Biochemistry	Alanine Aminotransferase	Screening, Day 30, Day 60	As per local practice	Quantitative	Local laboratory
		Aspartate Aminotransferase				
		Creatinine				

* Day 7 hematology testing will be performed if any ≥ Grade 1 for platelet decrease is detected on Day 1 after vaccination. Similarly, hematology testing on Day 37 will be performed if any ≥ Grade 1 for platelet decrease is detected on Day 31.

** **White Blood Cell differential including absolute neutrophil and lymphocyte counts must be recorded in the eCRF. (Amended 10 December 2017)**

Additional hematology and/or biochemistry testing may be performed or required in specific circumstances. Refer to Figure 2 for a schematic overview.

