7.5. Contraindications to subsequent vaccination

The following events constitute absolute contraindications to further administration of ChAd155-RSV vaccine. If any of these events occur during the study, the subject must not receive additional doses of vaccine but may continue other study procedures at the discretion of the investigator (see Section 9.5).

- Anaphylaxis following the administration of vaccine.
- Any confirmed or suspected immunosuppressive or immunodeficient condition, including HIV infection.
- Any condition that in the judgment of the investigator would make IM injection unsafe.
- Current autoimmune disease.
- Acute or chronic, clinically significant pulmonary, cardiovascular, hepatic or renal functional abnormality, as determined by physical examination or laboratory tests.
- Failure to thrive.

The following events constitute contraindications to administration of ChAd155-RSV vaccine at that point in time; if any of these events occur at the time scheduled for vaccination, the subject may be vaccinated at a later date, within the time window specified in the protocol (see Section 6.5), or the subject may be withdrawn at the discretion of the investigator (see Section 9.5).

- Acute disease and/or fever at the time of vaccination.
 - Fever is defined as temperature $\geq 37.5^{\circ}\text{C}/99.5^{\circ}\text{F}$ for oral, axillary or tympanic route, or $\geq 38.0^{\circ}\text{C}/100.4^{\circ}\text{F}$ for rectal route. The preferred route for recording temperature in this study will be axillary.
 - Subjects with a minor illness (such as mild diarrhea, mild upper respiratory tract infections) without fever can be administered all vaccines.
- Any Grade 1 abnormality with potential clinical relevance or any \geq Grade 2 abnormality in hematological parameters detected in the Day 7 blood sample (refer to Section 6.6.11.2, Figure 2 and Appendix C).

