2c	Any ≥ Grade 3 unsolicited AE in an investigational RSV vaccine group, that cannot reasonably be attributed to a cause other than vaccination, within the 7-day (Days 0-6) post-vaccination period OR Any ≥ Grade 3 abnormality in pre-specified hematological or biochemical laboratory parameters in an investigational RSV vaccine group, if it cannot reasonably be attributed to a cause other than vaccination, up to the Day 7 post-vaccination visit ¹	≥ 25% & ≥ 2 infants/group	≥ 25% & ≥ 2 infants/group	≥ 25% & ≥ 2 infants/group

[figure not shown]
¹ Refer to [Appendix C](#).

Of note, no formal holding rules will be applied for other safety data collected. However, these data will also be reviewed by the iSRC and the IDMC in order to allow for an overall assessment of the benefit/risk ratio of vaccination.

Risk assessment

Figure 4 gives the probability of not meeting holding rule 1-2 for 16 subjects per study group in each step.

Figure 4 Evaluations based on 16 subjects - Risk assessment curve for one formulation based on the proposed safety holding rules

The above figure illustrates that, with *a maximum of* 16 subjects per study group (Amended 10 December 2017):

- Each holding rule 1 (a - d) has more than 85% chance of not being met for vaccination with a true incidence rate below 1% and has more than 80% chance of being met for vaccination with a true incidence rate above 10%.
- Each holding rule 2 (a - c) has more than 90% chance of not being met for vaccination with a true incidence rate below 10% and more than 60% chance of being met for vaccination with a true incidence rate above 25%.

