11. STATISTICAL METHODS

11.1. Primary endpoint

- Occurrence of AEs from first vaccination (Day 0) up to Day 60.
 - Occurrence of each solicited local and general AE, during a 7-day follow-up period after each vaccination (i.e. the day of vaccination and 6 subsequent days).
 - Occurrence of any unsolicited AE, during a 30-day follow-up period after each vaccination (i.e. the day of vaccination and 29 subsequent days).
 - Occurrence of any SAE from Day 0 up to Day 60.
 - Occurrence of episode of spontaneous or excessive bleeding (AE of specific interest), during a 30-day follow-up period after each vaccination.
 - Occurrence of any hematological (hemoglobin level, white blood cells and platelets) laboratory abnormalities at Screening, Day 1, Day 7, Day 30, Day 31, Day 37, and Day 60.
 - Occurrence of any biochemical (alanine aminotransferase, aspartate aminotransferase and creatinine) laboratory abnormalities at Screening, Day 30, and Day 60.

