 - Blood samples for **biochemistry** will be taken from all infants at Screening (up to ~~14~~ **29** days before first vaccination to Day 0) and on Day 7, Day 30, Day 37, and Day 60 (refer to Table 11 for the list of parameters to be tested). Blood samples for **hematology** will be taken from all infants at Screening (up to ~~14~~ **29** days before first vaccination to Day 0) and on Day 1, Day 7, Day 30, Day 31, Day 37, and Day 60 (refer to Table 11 for the list of parameters to be tested). A clinical history and examination with special attention given to detection of spontaneous bleeding or easy bruising and evidence of bruising or petechiae will be performed on Day 1, Day 3 and Day 7 after each vaccination (i.e. Day 1, Day 3, Day 7, Day 31, Day 33, and Day 37). On Day 1, Day 7, Day 31, and Day 37, special attention will also be given to the detection of petechiae or evidence of petechiae induced by the tourniquet. Further testing may be required to investigate a finding or guide subject management based on the investigators clinical judgment. Subjects' parent(s)/LAR(s) will be instructed to contact the investigator/study staff if their child presents symptoms of spontaneous bleeding or easy bruising following vaccination. Refer to Section 6.6.11.2 and Figure 2 for information about the re-testing of samples in case of any Grade 1 abnormality with potential clinical relevance or any \geq Grade 2 abnormality.
- Surveillance for RSV-RTI, difficulty in breathing and wheezing episodes.

Surveillance period will be carried out from Visit 1 (after Dose 1) until Visit ~~10~~ **11** (Day ~~365~~**730**). In order to detect asymptomatic RSV-RTI, monthly nasal swabs for analysis at sponsor laboratory will be performed for all subjects during the RSV season. In order to timely detect RSV-RTI and to ensure cases are timely captured by the study sites, both active and passive surveillance will be conducted:

In **Section 4.1 RTI case definitions**, the following change has been made:

- During the analysis of the study, all cases identified during the surveillance of RSV-RTI will be definitively classified as either RTI, LRTI or severe LRTI according to the case definitions described in Table 4. ***The analysis may also be done using the available World Health Organization (WHO) case definitions for RTI, LRTI and severe LRTI.***

In **Section 4.2.1 Start date of the RTI episode**, the following change has been made:

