Amendment number:	Amendment 2
Amendment date:	08 June 2017
Co-ordinating author:	PPD (Scientific Writer, Keyrus Biopharma contractor for GSK Biologicals)
Rationale/background for changes:	

 • During initial implementation of this study, parents have given feedback that the number of visits and blood tests is challenging to accommodate with busy family schedules and is demanding for young children. This amendment reduces the burden on families whilst maintaining the intended close oversight of the potential risk of thrombocytopenia, by reducing the number and frequency of required blood tests and visits unless clinically required. Assessment of platelet counts (currently at Days 1, 7, 31 and 37) will now be repeated at Day 7 and/or Day 37 in those infants with a Grade 1 or greater abnormality detected at either Day 1 and/or Day 31. This is because the nadir of the platelet count occurred on the first day following dosing in the preclinical data. This modification of monitoring is judged by the Independent Data Monitoring Committee (IDMC) and GSK to be appropriate, as the sampling plan captures any potential initial fall and then subsequent recovery. The clinic visits at Day 3 and Day 33 including a clinical examination of the child for evidence of petechiae may be replaced by a phone call to inquire of the infants' general health and to solicit reports of a rash, spontaneous bleeding or easy bruising, which are all indicative of thrombocytopenia. As an additional safety measure the subjects' parent(s)/legally acceptable representative(s) (LAR[s]) will be instructed to contact the investigator/study staff immediately if their child develops a rash, in order to detect any thrombocytopenic petechiae or purpura. This will supplement the current instruction to report spontaneous bleeding or easy bruising in the month following vaccination. As there is no absolute requirement for sampling for hematology on Day 7 or 37, the other tests of biochemistry and cell mediated immunity (CMI) are not requested under this amendment at these timepoints. • It has been clarified that blood samples for CMI and for humoral immunogenicity may be postponed until after the RSV serostatus is known and eligibility is confirmed up to or on Day 0 (but before vaccination). • The age range for enrolment has been expanded an additional 6 months, from 12 to 17 months initially, to 12 to 23 months. These children are still at risk of respiratory syncytial virus (RSV) disease and could potentially benefit from this vaccine. This would also increase the number of subjects screened who are likely to be previously 	

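### On the per-dose reading of holding rule 2c, no scheduled biochemistry sample falls inside its window, so its biochemical trigger cannot fire from planned data

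*Protocol*

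**What the plan says.** The laboratory part of rule 2c in Table 22 covers Grade 3 or worse results in both haematology and biochemistry in a vaccine group, "if it cannot reasonably be attributed to a cause other than vaccination, up to the Day 7 post-vaccination visit". The threshold is at least 25% of the group and at least 2 infants. The note under the table says that other safety data are reviewed by the iSRC and IDMC but fall under no formal holding rule.

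Table 11 (Section 6.7.3) gives the biochemistry timepoints as "Screening, Day 30, Day 60". Section 11.1 matches this: "Occurrence of any biochemical (alanine aminotransferase, aspartate aminotransferase and creatinine) laboratory abnormalities at Screening, Day 30, and Day 60". For the Day 30 visit, Table 5 footnote g adds: "Blood samples to be taken before vaccination". So the Day 30 sample comes before Dose 2.

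The schedule used to be fuller. The Amendment 1 text in Appendix D has biochemistry at Screening "and on Day 7, Day 30, Day 37, and Day 60". The rationale for Amendment 2 then says that, with Day 7 and Day 37 haematology no longer mandatory, "the other tests of biochemistry and cell mediated immunity (CMI) are not requested under this amendment at these timepoints".

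**The concern.** A holding rule works only if the data it refers to are collected inside its window. Amendment 2 removed the only routine biochemistry that fell within 10 days of a dose. It aligned Table 11, the primary endpoint and the Day 7 laboratory contraindication in Section 7.5, which now mentions haematology only. Its change list covers Sections 9.10.2 to 9.10.4 and then goes to 11.1, leaving Section 9.10.5 as it was. Amendment 4 edited Section 9.10.5 but did not touch rule 2c.

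This is the first use of the vaccine in infants, with dose escalation. A reader of Table 22 would believe that Grade 3 liver or creatinine results in a quarter of a vaccine group trigger an automatic hold. On the per-dose reading, such results at Day 30 or Day 60 would instead be judged case by case, because the note under Table 22 places them outside the formal rules.

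**Working it through.** **1. The plan's own operating characteristics.** Section 9.10.5 describes the rules for 16 subjects per group. With X ~ Binomial(16, p), a group-2 rule needs X ≥ 4 (25% of 16) and a group-1 rule needs X ≥ 1.

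- Group 1, not met at p = 1%: 0.99^16 = 85.1% (stated: more than 85%).
- Group 1, met at p = 10%: 1 − 0.90^16 = 81.5% (stated: more than 80%).
- Group 2, not met at p = 10%: P(X ≤ 3) = 93.2% (stated: more than 90%).
- Group 2, met at p = 25%: P(X ≥ 4) = 59.5%; at p = 26%, 63.0% (stated: more than 60% above 25%).

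The stated figures reproduce. They presuppose that every vaccinee supplies a result inside the window.

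**2. Window against draws.** Intervals are from Table 6, counted in days after the relevant dose.

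| Dose | Window closes (Day 7 or Day 37 visit) | Next scheduled biochemistry | Smallest gap |
|---|---|---|---|
| Dose 1 | 7–10 | Day 30 visit: 23–36 | 23 − 10 = 13 days |
| Dose 2 | 7–10 | Day 60 visit: 28–35 | 28 − 10 = 18 days |

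The Day 30 sample precedes Dose 2, so it cannot serve as an early post-Dose 2 sample. Of the 2 scheduled post-dose draws, 0 fall in the window at any permitted visit timing. With scheduled samples only, the biochemical part is therefore met with probability 0 at any true rate, against 59.5% at a 25% rate if every vaccinee had a countable result.

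**3. The other reading.** The laboratory clause gives no start day and does not say that it applies after each dose. If it meant one window from Dose 1 to the Day 37 visit, that window would close 23 + 7 = 30 to 36 + 10 = 46 days after Dose 1. The Day 30 draw would then count. The Day 60 draw still would not.

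**4. What the fix would do.** Let p be the probability that an infant has a countable Grade 3 or worse biochemistry result across both draws. The documents give no such rate, so p is an assumption. The rule needs k = max(2, ⌈0.25n⌉): 4 of 16 or 2 of 8. The last row checks after every infant, using the vaccinees so far as the denominator, and is an upper bound.

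| Probability that the rule is met | p = 1% | 5% | 10% | 25% | 50% |
|---|---|---|---|---|---|
| 16 vaccinees, one look | <0.01% | 0.7% | 6.8% | 59.5% | 98.9% |
| 8 vaccinees, one look | 0.3% | 5.7% | 18.7% | 63.3% | 96.5% |
| 16 vaccinees, look after every infant | 0.3% | 6.2% | 21.7% | 74.9% | 99.5% |

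With 8 vaccinees, repeated looks change nothing, because the threshold is 2 at every count up to 8.

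**The case against.** The strongest reply has four parts.

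- **Some samples can count.** Table 5 allows biochemistry at an unscheduled safety visit, and Section 3 shows that there were samples "for subjects enrolled under protocol amendment 1", when Day 7 and Day 37 biochemistry was routine. This is correct. But unscheduled samples depend on who happens to be tested, which is a poor basis for a 25% threshold. The number of Amendment 1 infants is not given, and they do nothing for infants on the current schedule.
- **The window may be cumulative.** The wording does not exclude this, so the statement about Day 30 results is conditional on the per-dose reading. That reading is the natural one, because the other parts of rules 2a to 2c use a Day 0–6 window after vaccination. The Day 60 draw is outside on either reading.
- **Protection exists elsewhere.** The iSRC sees unblinded biochemistry about every three weeks, the IDMC sees laboratory toxicity monthly, and either finding any other safety signal puts vaccination on hold. Section 7.5 bars further doses in an infant with a clinically significant "hepatic or renal functional abnormality, as determined by physical examination or laboratory tests". All of this stands and limits the harm. None of it is a pre-set group-level trigger.
- **A later window changes the rule's character.** Three to five weeks after a dose, intercurrent illness or routine vaccines make attribution harder. This is a fair reason to prefer clarifying the text over extending the window. It is no reason to leave the text as it is.

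The committee charters are not available here and may set data cut-offs, but Table 22 should be workable as written.

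**Conclusion.** The concern holds. On the per-dose reading, none of the scheduled post-dose biochemistry in the current plan can meet rule 2c. On the cumulative reading, post-Dose 2 biochemistry still has no formal trigger. The haematology part works, because all infants are sampled on Days 1 and 31.

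The gap between windows and draws needs no assumption beyond the Table 6 intervals and the reading of the clause. The probabilities for the fix rest on assumed rates and on independent infants. Committee review and the per-infant contraindication keep this at the level of something that should be fixed.

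**What to change.** In Table 22, keep the Day 7 visit limit for haematology and state that it applies after each dose. For biochemistry, extend the window to the scheduled Day 30 sample, counted to Dose 1, and to the scheduled Day 60 sample, counted to Dose 2, including unscheduled samples in between. SAP Template 24 already labels the first of these (Day 31 in SAP numbering) as post-Dose 1. Keep the 25% and 2-infant threshold and the attribution clause.

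If the sponsor and IDMC prefer not to extend the window, Table 22 should say two things: that the biochemical part applies only to samples taken up to the Day 7 visit (unscheduled, or from Amendment 1 infants), and that Day 30 and Day 60 results are reviewed without a formal rule.

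Either change is protocol wording and needs no extra blood. Extending the window brings the added chance of a hold tabulated in the working, and harder attribution at the later draws. In Step 3 a Day 60 trigger may come after most dosing is done, so there the Day 30 sample gives most of the protection.
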